## **SIGNIFICANCE**

### **CA-S. aureus burden**

Community-associated *S. aureus* infections have become a significant public health problem throughout the United States. These infections span a wide range in severity from superficial skin abscesses to invasive pyomyositis, severe necrotizing pneumonia and fatal septicemia [7-11]. Recurrent *S. aureus* SSTI are problematic and recurrence rates have been reported in up to 50% of pediatric patients [12-16]. Recurrent *S. aureus* infections requiring emergency center care is common and accounts for significant utilization of hospital resources [17]. The incidence of *S. aureus* SSTI has risen dramatically over the past decade [18], such that cellulitis and soft tissue abscesses are the most frequent primary diagnoses associated with *S. aureus*. In 2005, there were 14.2 million outpatient clinic visits for SSTI (48.1 visits/1000 in the US) compared with just 8.6 million visits (32.1 visits/1000) in 1997 [18]. Due to this substantial burden, MRSA is a top priority for the Institute of Medicine's Comparative Effectiveness Research Program [19]. The annual economic burden of MRSA infection in the United States is approximately \$14 billion [20]. At SJH and MMC in Springfield, Illinois, we have seen a significant increase in the number of pediatric ED and EC visits. In the last five years there has been an average of 1400 visits a year for SSTI, which counts for more than a fifty percent increase during this time period.

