### **Management of CA-S. aureus abscesses**

It is controversial whether abscesses requiring incision and drainage also require antibiotics [28]. The frequency of antibiotic prescription in *S. aureus* SSTI is still common as described in the literature [29]. Creech et al surveyed over 100 Pediatric Infectious Diseases Consultants and found that all of them (N=197) prescribed antibiotics; no provider reported using incision and drainage alone without antibiotic therapy [30]. Mc Neil et al reported an almost 95% rate of antibiotic prescription among children with *S. aureus* SSTI at Texas Children's Hospital [31].

In a study done by Ruhe et al, patients with SSTIs caused by MRSA benefited from antibiotic treatment. Patients with CA-MRSA SSTI who received antibiotics in addition to incision and drainage had a greater treatment success rate (infection cure) than those managed with incision and drainage alone (95% versus 87%,  $P = .001$ ) [32]. In a randomized trial by Duong et al, treatment failure rates for CA-MRSA skin abscesses were similar after incision and drainage between patients who received antibiotics and those given a placebo. However, at 10-day follow-up, new lesions formed in 26.4% of cases in the placebo group and only 12.9% of cases in the antibiotic group [12]. Schmitz et al showed a similar incidence of treatment failure in adult patients with uncomplicated abscesses receiving trimethoprim-sulfamethoxazole versus placebo (17% vs 26%,  $P = .12$ ); but at 30-day follow-up the incidence of new lesions was lower in the antibiotic group compared to the placebo group (9% vs 28%,  $P = .02$ ) [33].

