Microbiology: Colonization swabs will be obtained at enrollment and at the 1 month follow-up visit by the PI or the research coordinator from the nose, axilla and inguinal folds. Four swabs will be used for each participant (1 each for both nostrils, both axillae, and both sides of the groin and the abscess site). Specimens will be collected with Copan E-swab™ Collection and Transport System to evaluate *S. aureus* colonization. This is a liquid-based multipurpose collection and transport system that maintains viability of aerobic, anaerobic and fastidious bacteria for 48 hours at room and refrigerator temperature. The research coordinator and I have successfully completed training for Shipping Infectious Materials and Biological Substances with SIU School of Medicine. Specimens will be shipped to Washington University in St. Louis, to the laboratory of [name] for microbiologic studies. If wound isolates from initial infection and a recurrence are available, they will be requested at the microbiology laboratory at SJH or MMC. After arrival, specimens will be incubated overnight in tryptic soy broth with 6.5% NaCl at 35°C. A sample of the broth will be plated to mannitol salt agar and incubated for 24-48 hours. Following confirmatory testing for *S. aureus* [37], susceptibility testing for cefoxitin (a surrogate for methicillin resistance) and 9 other antibiotics will be determined by Kirby-Bauer disk diffusion, in accordance with published guidelines [37]. Inducible clindamycin resistance will be tested [38]. All isolates will be stored in glycerol at -20°C.

Sample size: This is a pilot study to determine the feasibility of recruiting patients as described, having them return for 1 follow-up visit, and collaborating with Washington University for future

investigations. Our goal is to get preliminary data. According to available billing records (ICD-9 codes), since 2010, there has been in average 130 pediatric visits per month at SJH, MMC ED and Express Cares secondary to SSTI. Our goal is to recruit 50 patients in 12 months, which means that we will need about a 30% success rate for recruitment (**Figure 3**). A sample size estimate was performed to evaluate the power in the study. Considering an incidence of recurrent SSTI of 50% in patients who did not receive antibiotic therapy, a 60-75% percent reduction of recurrent SSTI (12-20% incidence) can be shown with 50-80% power.

[figure not shown]

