### Specific Aim 2:

#### *Primary outcome:*

To measure incidence of SA recurrent skin and soft tissue infections at 3 months in patients who did or did not receive systemic antibiotic therapy. A binary logistic regression will be performed to see if antibiotic therapy is associated with SSTI at 3 months after adjusting for covariates.

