### Potential limitations:

Recruitment success rate is estimated to be around 30% in order to collect the desired patient sample (50 patients) in a 1 year period; this is based on a prior study in which the same population was targeted [39]. We recognize the complexity of having patients come to clinic for research purposes only in follow up. SIU School of Medicine's Department of Pediatrics is providing funds to complete the study beyond the 12 month period. Patient reimbursement of a \$20 check will be given at the follow-up visit for study purposes, without any charges to medical insurance. In previous studies conducted by our team, we had had a high longitudinal retention rate when the same incentive was given [39, 40]. Specimens will be obtained by research personnel and the collection technique. The surface area swabbed and the pressure used will be standardized for all participants. We have validated the shipping procedures for specimen transport to our collaborators at Washington University. We would like to evaluate whether shipment of the swabs can be done in a timely manner and whether the length of time required for shipment impacts the ability to successfully recover microorganisms. Reaching participant for follow-up phone calls may be a challenge, especially at 6 and 12 months after study enrollment; thus, we will obtain multiple methods of contact for each participant. A source of bias that we will have is the variability in the treating physician's decision to administer antibiotics or not. Adjusting for possible confounding factors and covariates will be made but these factors will not play a role in the primary outcome which is *S. aureus* colonization.

**Conclusion:** The Research Seed Grant, RSG, is an important step in achieving my career goal of becoming an independent investigator at SIU and will offer me a tremendous opportunity to help our patient population. The goal of this project is to obtain preliminary data which will allow me to apply for future external funding to be able to recruit more patients and to show a statistical significance. Recurrent *S. aureus* SSTI have become a major source of morbidity in our pediatric population. Decreasing the number of recurrent SSTI will decrease ED and PCP clinic visits and will benefit our public health.

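### Does the 50-80% power claim for recurrent SSTI fail because it assumes 50% recurrence without antibiotics, the top of the reported range?

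*Combined protocol and SAP*

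**What the plan says.** The Sample size paragraph describes a pilot to test feasibility and gather preliminary data: "Our goal is to recruit 50 patients in 12 months". It then gives a conditional power statement. The condition is "Considering an incidence of recurrent SSTI of 50% in patients who did not receive antibiotic therapy", and the result is that "a 60-75% percent reduction of recurrent SSTI (12-20% incidence) can be shown with 50-80% power". It names no source for the 50%, and no time point, group split or test.

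Three other places bear on the 50%:

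- The section on CA-S. aureus burden says that "recurrence rates have been reported in up to 50% of pediatric patients [12-16".
- Management of CA-S. aureus abscesses cites a randomized trial in which, at 10 days, "new lesions formed in 26.4% of cases in the placebo group and only 12.9% of cases in the antibiotic group [12". It also cites an adult trial in which "at 30-day follow-up the incidence of new lesions was lower in the antibiotic group compared to the placebo group (9% vs 28" percent.
- The primary outcome of Specific Aim 2 is "To measure incidence of SA recurrent skin and soft tissue infections at 3 months in patients" with and without systemic antibiotics, analysed by adjusted logistic regression.

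The Conclusion says the project is meant to "obtain preliminary data which will allow me to apply for future external funding to be able to recruit more patients".

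**The concern.** The 50% appears to be the top of a reported range. That range covers pediatric patients in general, not untreated children, and has no time horizon. The document also cites two direct comparisons of untreated and treated patients, with untreated rates of 26.4% and 28%, and the power statement uses neither. The trial behind the 26.4% is one of the sources cited for the range that reaches 50%.

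If those lower rates applied to Aim 2, 50 children would have well under 50% power. The expected 95% confidence interval for the risk difference would include zero, and a null result might be misread as no benefit from antibiotics. A later study planned on 50% v 12-20% would need 42 to 88 children in all for 80% power, against 126 to 294 at the cited rates.

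**Working it through.** **Inputs.** N = 50 and 50% v 12-20% come from the Sample size paragraph. The pairs 26.4% v 12.9% (10 days) and 28% v 9% (30 days, adults) come from Management of CA-S. aureus abscesses. The significance level is 0.05 (Data Analysis Plan). Three assumptions are made: two-sided testing, because the plan names no one-sided test and refers to a 95% interval; complete follow-up; and no covariate adjustment.

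**Method.** For n1 untreated and n2 treated children, power = sum over all (x, y) of Bin(x; n1, p1) × Bin(y; n2, p2), counting tables with p < 0.05. Results are Fisher / uncorrected chi-square.

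**1. The plan's own figure.** A 60% reduction from 50% is 0.50 × 0.40 = 20%. A 75% reduction is 0.50 × 0.25 = 12.5%, given as 12%.

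| Untreated v treated | Power at 25/25 |
|---|---|
| 50% v 20% | 0.51 / 0.64 |
| 50% v 12% | 0.77 / 0.87 |

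The stated 50-80% is about right. An exact match cannot be settled without the split and test.

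**2. The cited rates, taken as they stand.**

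| Pair | Relative reduction | Power at 25/25 | Best over splits 2:48 to 48:2 |
|---|---|---|---|
| 26.4% v 12.9% | 1 − 12.9/26.4 = 51% | 0.135 / 0.235 | 0.20 / 0.27 |
| 28% v 9% | 1 − 9/28 = 68% | 0.29 / 0.435 | 0.39 / 0.47 |

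The 95% half-width at 25/25 is 1.96 × √[p1(1−p1)/25 + p2(1−p2)/25]. It is 21.7 points around a difference of 13.5, and 20.9 around 19.0. Both intervals include zero.

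**3. Baseline or effect?** Keep 50% untreated and apply each cited reduction at 25/25.

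- 68% reduction: 50% v 16.1%, power 0.64 / 0.76, inside the stated range.
- 51% reduction: 50% v 24.4%, power 0.37 / 0.50, at or below its lower end.

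For the adult trial, the shortfall in step 2 therefore comes from the baseline rate. For the 10-day trial it comes from both the baseline and the smaller effect.

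**4. The time horizon.** The cited pairs stop at 10 and 30 days, and Aim 2 is judged at 3 months. Cumulative risk can only rise, so the effect of the gap depends on what happens afterwards. Two assumptions bracket it.

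- *Constant hazard in each group, 30-day pair.* At 90 days, untreated 1 − 0.72³ = 62.7% and treated 1 − 0.91³ = 24.6%, a 61% reduction. Power at 25/25 is 0.74 / 0.83. At 60 days, 1 − 0.72² = 48.2% and 1 − 0.91² = 17.2%, with power 0.55 / 0.68.
- *No antibiotic effect after the cited time point, untreated risk reaching 50% at 3 months.* From the 30-day pair, treated risk is 1 − 0.91 × (0.50/0.72) = 36.8%, with power 0.11 / 0.18. From the 10-day pair it is 1 − 0.871 × (0.50/0.736) = 40.8%, with power 0.07 / 0.12.

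Constant hazard cannot sensibly be applied to the 10-day pair: over nine 10-day periods it gives 1 − 0.736⁹ = 93.7% untreated, which is implausible.

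The documents hold nothing that chooses between these paths. Power at 3 months could lie in or near the stated range, or far below it.

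**The case for a change.** The strongest case for a change is that a plan which states power should base it on supported inputs. The 50% carries no source, and the only 50% in the visible text is an upper limit for a broader group. Aim 2 has its own primary outcome and a significance test. The result in step 2 needs no assumed split, prescribing rate or dropout, and loss to follow-up would only lower power. Labelling 50% as an upper value and adding power at the cited rates would take a few sentences and no extra patients.

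Part of this stands. The 50% is optimistic or at least unsupported in the visible text, and a reader cannot tell which split, test or time point lies behind the range. The below-50% result also holds under two-sided testing, although one-sided testing at 0.05 would lift the adult pair to 54.7% at its best split.

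The rest does not carry. The cited rates do not estimate 3-month recurrence in children, so printing 14-24% and 29-44% power beside that endpoint would exchange an unsupported baseline for a mismatched one. The larger sample sizes for a later study matter only if the planning inputs are carried forward unchanged, which the document does not say. The Data Analysis Plan already provides frequencies by antibiotic group, including the follow-up questionnaires, so the observed risks and the untreated share will be available to anyone planning that study.

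**Conclusion.** The concern does not call for a change. The power statement is conditional on an openly stated 50%, and its arithmetic is about right: 0.51 to 0.87 across both ends and both tests with equal groups. At the shorter-term rates the document cites, two-sided power peaks at 0.27 and 0.47. Those rates are for 10 days and for adults at 30 days, and extending the 30-day pair to 3 months gives anything from 0.11 to 0.83 depending on the assumption made. That makes 50% a debatable planning value, not an error.

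Little depends on it here. The study is a pilot with a fixed target of 50. Potential limitations names colonization as the primary outcome, and the Conclusion says that showing statistical significance awaits a larger study. A range that starts at 50% power already tells the reader that Aim 2 is weak. A different baseline would leave the sample size, visits, tests and conclusions as they are. The missing source, time point, split and test are reporting details that an analyst can supply.

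This rests on two-sided testing at 0.05, complete follow-up and unadjusted comparison. It also rests on the visible text, which may not include the source of the 50%.

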### Data Analysis Plan

Data on *S. aureus* identification will be collected from Washington University School of Medicine and recorded, along with questionnaire and clinical variables, on a data collection form by the principal investigator and research coordinator and then transferred to an excel spreadsheet for statistical analysis. Statistical Package for the Social Sciences (SPSS), version 20, will be used for data analysis.

Descriptive Statistics will be computed for all study variables. Continuous variables will be described with measures of central tendency (mean, median) and dispersion (range, standard deviation). Categorical variables will be summarized as frequencies and percentages.

We will calculate the frequencies/percentages for patient demographics, clinical characteristics, baseline questionnaire, follow-up questionnaires, and *S. aureus* colonization (nose, axilla, and inguinal folds) for each group: 1) Systemic antibiotic therapy 2) No systemic antibiotic therapy. Characteristics will be compared using independent t-tests for continuous variables and Chi-squared tests of independence for categorical variables. Significance will be assumed when  $p < 0.05$  or the 95% confidence interval.

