Data Collection: At study enrollment, a detailed questionnaire will be administered to identify risk factors for *S. aureus* colonization, infection, and transmission. Clinical data will be collected as well to track clinical signs at the time of presentation (vital signs, body site of infection, size of abscess, presence of systemic symptoms, type of incision and drainage, antibiotic use, type of packing applied). In addition, colonization swabs from the nose, axilla, inguinal folds and wound isolate will be collected and transported to [name] laboratory at Washington University. Longitudinal study visits will be conducted at the SIU Pediatric Infectious Disease Clinic one month following enrollment for research purposes only by PI or by the research coordinator. At this visit, a follow-up questionnaire will be administered inquiring about new, recurrent, or relapsed infection. Colonization swabs will be obtained and transported to [name] laboratory. Also history of any household members with any recent SSTI will be asked. Follow-up phone calls will be administered at 3, 6 and 12 months after enrollment to ask about recurrent infections. If an interval infection did occur, we will collect data regarding whether the individual sought medical care (and if so, the location where medical care was sought), the date of infection, the body site of infection, the bacteria causing infection, if known, whether the individual required a drainage procedure, surgery, or hospitalization, and whether the participant received antibiotics, oral or intravenous. If the patient sought medical care, records from the hospital and/or provider's office will be obtained for verification. Again, question about any household member having an SSTI will be made. Throughout the longitudinal study, we will ask participants to contact us if they develop a SSTI. The participant will be directed to seek medical treatment from their primary healthcare provider.

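### Nothing in the plan separates knowledge of index antibiotic treatment from the eliciting and coding of recurrent infection; Aim 2 is the aim mainly exposed.

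*Combined protocol and SAP*

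**What the plan says.** The plan compares children who did and did not receive systemic antibiotics, as chosen by the treating physician.

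- **Exposure.** The enrollment data in the Data Collection paragraph include "size of abscess, presence of systemic symptoms, type of incision and drainage, antibiotic use, type of packing applied".
- **1-month visit.** It is conducted "one month following enrollment for research purposes only by PI or by the research coordinator", and at it "a follow-up questionnaire will be administered inquiring about new, recurrent, or relapsed infection". The Microbiology paragraph gives the swabbing to the same roles: "Colonization swabs will be obtained at enrollment and at the 1 month follow-up visit by the PI or the research coordinator".
- **Later follow-up.** "Follow-up phone calls will be administered at 3, 6 and 12 months after enrollment to ask about recurrent infections". The caller is not named. Families are also asked to make contact themselves if an infection occurs.
- **Details of an episode.** The listed items include whether and where care was sought, date, body site, organism where known, procedures and antibiotics. Provider records are obtained for verification if care was sought.
- **Recording.** Under the Data Analysis Plan, culture results are "recorded, along with questionnaire and clinical variables, on a data collection form by the principal investigator and research coordinator", then moved to a spreadsheet.
- **Safeguards for colonization.** Culture and susceptibility testing are done at a separate institution. Potential limitations adds: "The surface area swabbed and the pressure used will be standardized for all participants".

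No masking of interviewer, swab-taker, data recorder or laboratory is described. The one source of bias named under Potential limitations is the physician's choice to prescribe.

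**The concern.** The Aim 2 primary outcome is *S. aureus* recurrent infection at 3 months, and its first step is a conversation. If the person asking, or the person later coding the answer, knows the index treatment, the depth of probing and the decision to count a doubtful episode can differ between groups. Any such difference enters the antibiotic contrast directly. The covariate adjustment planned for Aim 2 addresses which children received antibiotics. It does not address how their recurrences were found and counted.

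The results are meant as preliminary data for a larger funding application, so a distorted recurrence contrast could carry into the planning of the next study.

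**Working it through.** **Step 1. Who knows what, and when.** The documents state no figure for this point, so the main check is a reading of the text.

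| Task | Who, per the documents | Separated from treatment group? |
|---|---|---|
| Record index antibiotic use | PI and coordinator | It is the exposure |
| 1-month questionnaire and swabs | PI or coordinator | Not described |
| Calls at 3, 6 and 12 months | Not stated | Not described |
| Culture and susceptibility | Outside laboratory | Not stated whether specimens are coded |
| Enter questionnaire and culture data | PI and coordinator | Not described |
| Decide that an episode counts as *S. aureus* recurrence | Not stated | Not described |

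**Step 2. Where judgement can enter Aim 2.**

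- *Eliciting.* An episode enters by questionnaire, phone call or the family's own contact. Record verification can confirm a reported episode for which care was sought. It gives no check on an episode that was never reported, or was managed without care.
- *Counting.* The follow-up questionnaire covers new, recurrent and relapsed infection without defining these terms. The outcome is recurrence due to *S. aureus*, yet the organism may be unknown. Someone must decide how such episodes are classified, and no rule is given.

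**Step 3. Where it can enter Aim 1.** Only through how the swab is taken, how the result is entered, or a laboratory that knows the group. Standardized swabbing and outside culture narrow the first and leave little room for judgement by study staff.

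**Step 4. Illustration of size.** Assume no true antibiotic effect.

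Observed rate = true rate × probability that a true recurrence is elicited and recorded.

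Inputs:

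- True rate 50% in both groups. This is the Sample size paragraph's rate without antibiotics; it carries no time horizon there, so using it at 3 months is an assumption. A lower rate of 30% is also assumed.
- Detection 90% in untreated and 70–80% in treated children, both assumed. The documents give no detection rates.

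Results:

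- At 30%: 0.30 × 0.90 = 27% untreated, against 0.30 × 0.70 to 0.80 = 21–24% treated.
- At 50%: 0.50 × 0.90 = 45% untreated, against 0.50 × 0.70 to 0.80 = 35–40% treated.
- Apparent ratio: 0.70/0.90 = 0.78 to 0.80/0.90 = 0.89, a false relative reduction of 11–22%.
- Absolute gap: 3–10 percentage points, or 0.75 to 2.5 children in an assumed group of 25.

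The same gap the other way round would give ratios of 0.90/0.80 = 1.13 to 0.90/0.70 = 1.29, making antibiotics look harmful.

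**Step 5. Effect on a test.** For an unadjusted Pearson chi-squared test at nominal two-sided 0.05, with an assumed 25 per group, exact enumeration gives these chances of a false positive:

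| True rate | Detection 90% in both groups | 90% v 80% | 90% v 70% |
|---|---|---|---|
| 30% | 0.054 | 0.061 | 0.084 |
| 50% | 0.064 | 0.079 | 0.128 |

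The planned Aim 2 analysis is an adjusted logistic regression, so these values indicate scale only.

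**The case against.** The strongest reply is that much of the concern rests on what the plan leaves unsaid.

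- A reader might infer that the interviewer has the child's treatment in view on a single form. The text does not say so. The data collection form may only be where answers are transcribed, and baseline and follow-up questionnaires are listed separately. Follow-up sheets may already carry no treatment information.
- A reader might infer that the same two people make the 3-month call. The caller is simply not named.
- A reader might infer that the question is open-ended, or that the interviewer rules on each lesion. No question wording is given, several items per episode are specified, and no one is assigned that ruling.
- Families can report unprompted, so recurrence does not depend wholly on the interviewer.
- Colonization, which Potential limitations calls the primary outcome, is cultured elsewhere from standardized swabs.
- The illustrated reduction of 11–22% is far below the 60–75% in the Sample size paragraph, and unmasked follow-up is ordinary in a 50-patient observational pilot.

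All of this stands as a limit on the claim. It does not remove the gap: the plan has no step that keeps index treatment apart from the eliciting and coding of recurrence, and no definition that would constrain the coding. Unprompted reports add episodes but do not settle how they are counted.

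**Conclusion.** The point holds as a gap in procedure, mainly for Aim 2. That the person asking or coding knows the group is a reasonable inference from the roles described, not a statement in the documents.

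Two stronger readings are not supported. The first is that all outcomes are equally exposed: the outside laboratory and standardized swabbing make Aim 1 much less so, with coding of specimens as the remaining question. The second is that results will drift toward a benefit of antibiotics. The plan asks whether antibiotics prevent recurrence and assumes a reduction in its power statement, but neither fixes the direction of any recording bias.

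The 11–22% and the false-positive rates rest on assumed detection rates, recurrence rates and group split; they show that a plausible gap would be modest but not negligible. No sample size or power figure changes. This is a cheap improvement and does not invalidate the pilot.

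**What to change.** In the Data Collection paragraph and the Data Analysis Plan:

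1. Use follow-up questionnaires and call sheets that carry the study number and no index-treatment information. Ask fixed-wording questions about skin and soft tissue infection before any question about antibiotics. State who makes the calls.
2. Define recurrence in advance, including how an episode with unknown organism is classified. Code it yes or no at each time point from call sheets and records, without reference to index treatment. Lock that variable before antibiotic group is merged into the spreadsheet.
3. Where feasible, have the staff member who did not enroll the child do the follow-up, and send specimens to the laboratory without treatment group.
4. Under Potential limitations, state that masking is partial: there are only two staff, both may have recorded enrollment data, retrieved records may mention treatment, and families know what was given.

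The cost is an extra form, a short procedure note and a small scheduling burden. No added visits are needed. Reporting differences that arise from the families themselves would remain.
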